10.5 Evaluating Adverse Events

10.5.1 Assessment of Intensity

The investigator or medically qualified designee will make an assessment of intensity for each AE reported during the study and will assign it to one of the following categories:

- Mild: An event that is easily tolerated by the subject, causing minimal discomfort and not interfering with everyday activities.
- Moderate: An event that is sufficiently discomforting to interfere with normal everyday activities
- · Severe: An event that prevents normal everyday activities.

NOTE: An AE that is assessed as severe should not be confused with an SAE. Severe is a category utilized for rating the intensity of an event; and both non-serious AEs and SAEs can be assessed as severe. For example, a headache may be severe (interferes significantly with the subject's usual function) but would not be classified as serious unless it met one of the criteria for SAEs, listed above. An event is defined as 'serious' when it meets at least 1 of the predefined outcomes as described in the definition of an SAE, NOT when it is rated as severe.

10.5.2 Assessment of Causality

The causality assessment is one of the criteria used when determining regulatory reporting requirements. For each AE (serious and non-serious), the investigator (or medically qualified designee) must provide an assessment of causality on the AE CRF page and the SAE form (subject to the classification of the AE). The investigator will also document in the medical notes that he/she has reviewed the AE and assessed causality, where applicable.

A "reasonable possibility" of a relationship conveys that there are facts, evidence, and/or arguments to suggest a causal relationship, rather than a relationship cannot be ruled out. Generally, the facts (evidence) or arguments to suggest a causal relationship should be provided.

The investigator will use clinical judgment to determine the relationship and will also consult the Investigator Brochure (IB), Safety Statement and/or Product Information, for marketed products, in the determination of his/her assessment. Alternative causes, such as underlying disease(s), concomitant therapy, other risk factors, and the temporal relationship of the event to the study product will be considered and investigated.

For each AE/SAE, the investigator must document in the medical notes that he/she has reviewed the AE/SAE and has provided an assessment of causality.

The investigator's assessment of causality must be provided for all AEs (serious and nonserious); the investigator must record the causal relationship in the CRF, as appropriate, and report such an assessment in accordance with the SAE reporting requirements if applicable.

There may be situations when an SAE has occurred and the investigator has minimal information to include in the initial report to GSK. However, it is very important that the investigator always make an assessment of causality for every event prior to the initial transmission of the SAE data to GSK CH. The investigator may change his/her opinion of causality in light of follow-up information and send an SAE follow-up report with the updated causality assessment.

10.6 Follow-up of Adverse Events

After the initial report, the investigator is required to proactively follow up with each subject and provide further information on the subject's condition.

All AEs (serious and non-serious) will be followed until resolution, or until the condition stabilizes, or until the event is otherwise explained, or until the subject is lost to follow-up.

The investigator is obligated to perform or arrange for the conduct of supplemental measurements and/or evaluations as may be indicated or as requested by GSK CH to elucidate as fully as possible the nature and/or causality of the AE. This may include additional laboratory tests or investigations, histopathological examinations, or consultation with other health care professionals.

New or updated information will be recorded on the AE CRF page and on the SAE form (subject to the classification of the AE).

The investigator will submit any updated SAE data to GSK CH within 24 hours of receipt of the information.

Investigators are not obliged to actively seek AEs in former subjects. However, if the investigator learns of a SAE, including death, at any time after a subject has been discharged from the study, and considers the event reasonably related to the study product or study participation, the investigator will promptly notify GSK CH by emailing the information to the GSK CH Clinical Operations Safety Reporting email box (PPD).

The GSK CH Study Manager or designee will be responsible for forwarding the information to the Case Management Group, Global Clinical Safety and Pharmacovigilance group mailbox at GSK (PPD).

The investigator will submit any updated SAE data to GSK CH within the designated reporting time frames.

10.7 Withdrawal Due to an Adverse Event

Withdrawal due to AEs should be distinguished from withdrawal due to other causes, according to the definition of an AE noted earlier, and recorded on the appropriate AE CRF page.

When a subject withdraws because of an SAE, the SAE must be reported in accordance with the reporting requirements defined.

10.7.1 Sponsor's Reporting Requirements to Regulatory Authorities and Ethics Committees

GSK CH has a legal responsibility to notify, as appropriate, the local regulatory authority and other regulatory authorities about the safety of a product under clinical investigation. Prompt notification of SAEs by the investigator to GSK CH is essential so that legal obligations and ethical responsibilities towards the safety of subjects are met.

GSK CH will comply with country specific regulatory requirements relating to safety reporting to the regulatory authority, IRB/EC and investigators.

Investigator safety reports must be prepared for suspected unexpected serious adverse reactions (SUSAR) according to local regulatory requirements and sponsor policy and forwarded to investigators as necessary.

An investigator who receives an investigator safety report describing a SAE or other specific safety information e.g. summary or listing of SAE from the sponsor will review and then file it along with the Investigator's Brochure in the investigator study master file, and will notify the IRB/IEC, if appropriate according to local requirements.

10.8 Pregnancy

10.8.1 Time Period for Collecting Pregnancy Information

Pregnancy information will be collected on all pregnancies reported while a female subject is participating in the study from the signing of informed consent until at least 21 days after last administration of study product.

10.8.2 Action to be Taken if Pregnancy Occurs

The investigator will collect pregnancy information on any subject who becomes pregnant while participating in the study after administration of the investigational product. The investigator will record pregnancy information on the appropriate form and submit it to CRO within 24 hours of learning of the subject becoming pregnant. The subject will be followed to determine the outcome of the pregnancy. Information on the status of the mother and infant/neonate (including concomitant medications taken by the mother during the pregnancy) will be forwarded to CRO. Generally, follow-up will be no longer than 6 to 8 weeks following the estimated delivery date. Any termination of the pregnancy will be reported.

CRO will scan and email the pregnancy form to the Case Management Group, Global Clinical Safety and Pharmacovigilance group mailbox at GSK CH (PPD)) with copy to the appropriate GSK CH Study Manager. Original pregnancy information forms will be retained in the investigator study master file.

11 DATA MANAGEMENT

As used in this protocol, the term case report form (CRF) is understood to refer to either a paper form or an electronic data record or both, depending on the data collection method.

For this study, subject data will be entered into an electronic CRF (eCRF), using a validated system. Data relating to SAEs, pregnancy and incidents will also be collected on paper forms.

The investigator is responsible for verifying that data entries are accurate and correct by physically or electronically signing the CRF.

GlaxoSmithKline Consumer Healthcare Confidential Template Version Effective: 18-May-18 (CCR #11475) Page **49** of **64**

The source documents (e.g. hospital records, clinical and office charts, laboratory notes, memoranda, evaluation checklists, pharmacy dispensing records, recorded data from automated instruments, microfiches, photographic negatives, microfilm or magnetic media, x-rays, subject files and records kept at the pharmacy, at the laboratory and at the medico-technical departments involved in the clinical study) which contain the source of data recorded in the CRF should be specified in Section 8 and 9. The CRF can be used as a source document at the discretion of data management.

Each subject will be assigned and identified by a unique Screening Subject Number. Any reference made to an individual subject within the study must be done using their unique Screening Subject Number.

11.1 Case Report Form

A CRF is a printed, optical, or electronic document designed to record the protocol required information to be reported to the sponsor on each trial subject.

For each subject who has given informed consent/assent the CRF must be completed and signed by the Principal Investigator (or authorized designee) to certify that the data are complete and correct. The investigator must maintain accurate documentation (source data) that supports the information entered in the CRF.

Management of clinical data will be performed in accordance with Third Party BDM Vendor applicable standards and data cleaning procedures with oversight by GSK CH to ensure integrity of the data, for example, to remove errors and inconsistencies in the data.

To protect the privacy of subjects, no Personally Identifiable Information (PII) (including the subject's name or initials or full birth date) is to be recorded in the CRF or as part of the query text.

All CRF pages should be completed during a subject assessment when the CRF has been designated as the source. Data that is sourced elsewhere should be entered into the CRF in an agreed upon timeframe between the Investigator and Sponsor.

GSK CH will obtain and retain all CRFs and associated study data as applicable at the completion of the study.

11.2 Data Handling

Documentation of all data management activities should allow step-by-step retrospective assessment of data quality and study performance.

Any changes or corrections to data will be performed in the Electronic Data Capture (EDC) System, and it will include rationale for changes. The EDC system has an audit trail, which will provide a complete record of the changes and corrections endorsed by the Investigator.

Adverse events will be coded using Medical Dictionary for Regulatory Activities (MedDRA) and any concomitant medications terms (if applicable) using an internal validated medication dictionary,

11.2.1 Data Queries

Programmed edit checks will be generated automatically, as the data are being entered into the system. Reports and listings on the CRF data will also be run, in addition to the queries already programmed and generated by the system, to raise manual queries as needed for site clarification or correction. The Clinical Dictionary Development and Management Group will

GlaxoSmithKline Consumer Healthcare Confidential Template Version Effective: 18-May-18 (CCR #11475) Page 50 of 64

raise queries as needed on safety data to code the terms (AEs and Drugs or concomitant medication) appropriately.

The study monitor will perform ongoing review the of the CRFs in accordance with the monitoring plan, to confirm that data entered into the CRF by authorized site personnel are accurate, complete, and verifiable from source documents; that the safety and rights of participants are being protected; and that the study is being conducted in accordance with the currently approved protocol and any other study agreements, ICH GCP, and all applicable regulatory requirements.

Any queries will be generated in the EDC System to the Investigator or designee, enabling the errors to be addressed in parallel with Data Management review. The study monitor can also run reports and listings on the CRFs, to raise manual queries as needed for site clarification or correction.

11.3 Processing Subject Reported Outcomes

Paper based subject reported outcome (PRO) data may be collected from a diary, questionnaire, or other specified document, etc. and entered into the data management system (DMS).

All PRO source data should be reviewed by the study staff and the study monitor in order to ensure accurate transcription of data and that any potential AEs or concomitant medications reported on these documents are discussed with the subject and transcribed accurately to the CRF and/or DMS. Site staff cannot make any changes to subject diaries. If a subject makes a change to the subject diary, they must initial and date the change. PROs that are classed as source data will be retained by the investigator and true/certified copies may be sent to a designated vendor or GSK CH as required.

To protect the privacy of subjects, no Personally Identifiable Information (PII) (including the subject's name or initials or birth date) is to be recorded on any PRO/ePRO that will be forwarded to GSK CH or Third-Party Vendor.

12 STATISTICAL CONSIDERATIONS AND DATA ANALYSES

12.1 Sample Size Determination

Approximately 300 subjects will be randomized to ensure at least 240 evaluable subjects complete the study for the PP analysis population. A maximum of 40 randomized subjects per center will be allowed.

Approximately 120 subjects per treatment arm has been determined to provide 80% power to demonstrate non-inferiority of DDEA 2.32% gel b.i.d with DDEA 1.16% gel q.i.d. by comparing the two-sided 95% CI of the difference in mean change from baseline of VAS POM score between the two products with the non-inferiority margin of 13 mm. This assumes a treatment standard deviation of 22mm and allows for a possible small true treatment difference of 5mm in favor of DDEA 1.16%.

The margin of 13 mm (on a 100 mm VAS scale) was chosen as the literature reported minimally important clinical difference for an acute musculoskeletal injury (Todd et al 1995), with treatment differences smaller than 13mm considered as not clinically important. The standard deviation was obtained from a previous placebo-controlled ankle sprain study VOPO-P-307 with DDEA 2.32% gel.

12.2 Statistical Methods and Analytical Plan

Additional details of the proposed statistical analysis will be documented in the statistical reporting and analysis plan (RAP), which will be written following finalization of the protocol and prior to study unblinding.

12.2.1 Definition of Analysis Populations

The safety population will include all subjects who are randomized and have received at least one dose of investigational product.

The modified intent-to-treat (mITT) population will consist of all randomized subjects who have at least one post baseline POM VAS assessment

The PP population includes all subjects from the mITT population who do not have any major protocol deviations that could confound the interpretation of the efficacy analyses. Protocol deviations that would exclude subjects from the PP population are defined in Section 12.2.2.

Before the study is unblinded, each actual post-baseline visit will be mapped to the target visit date to which it is chronologically closest. This corresponds to the following visit windows: Visit 2 (Days 2–4), Visit 3 (Days 4–6), Visit 4 (Days 7+). The numbering of the actual visits (from Visit 1 to Visit 4) will then be changed as needed to improve the correspondence of the actual visit dates to the protocol-specified schedule of visits, particularly in relation to Visit 3 (primary). Final determinations will also be made and documented before the study is unblinded to address visits that occur on Day 4 (which maps to two visit windows) or visits occurring well beyond the target date for the final visit or any other irregularities. Further detail is provided in the statistical analysis plan.

12.2.2 Exclusion of Data from Analysis

Exclusion of any data from the analyses will be determined during a Blind Data Review Meeting prior to database lock. Any reasons for exclusion from an analysis population will be listed, if applicable.

Protocol deviations that would exclude subjects from the PP population may include (but are not limited to) the following:

- Subjects failing to meet inclusion and exclusion criteria but were included in the study.
- Subjects without a Day 5 pain on movement VAS assessment
- Subjects with poor or moderate compliance with study treatment
- Subjects taking prohibited medication
- Subjects identified with other major protocol deviations

Further detail is provided in the statistical analysis plan.

12.2.3 Demographic and Baseline Characteristics

Demographic data, including age, gender and race, and other baseline data will be presented using descriptive statistics.

Categorical variables will be summarized by the number and percentage of subjects with each relevant characteristic. Continuous variables will be summarized by calculating the mean, standard deviation, median, minimum and maximum.

GlaxoSmithKline Consumer Healthcare Confidential Template Version Effective: 18-May-18 (CCR #11475) Page **52** of **64**

12.2.4 Study Drug/Product Compliance and Use of Other Therapies

12.2.4.1 Study Drug/Product Compliance

Compliance is defined in terms of the total weight of study medication used and total number of applications made as follows:

- Good: > 80% of the gel has been applied and > 80% of scheduled applications made,
- Moderate: not Good and not Poor
- Poor: < 50% of the gel has been applied or < 50% of scheduled applications made.

The % of gel used will be computed relative to the actual number of applications made from randomization through the final visit multiplied by 2 g. This value is to be recorded in the CRF. Scheduled applications will include all scheduled applications through the day before the final visit. On day 1, the percentage of gel used will be calculated based on the possible number of administrations on that day. If only 3 were possible, then 100 % compliance on that day will be considered 3 applications.

Compliance will be summarized descriptively as (1) % of scheduled applications made, (2) % of gel used relative to number of actual applications * 2g, and (3) compliance category (Good/Moderate/Poor). Exposure to study drug will be summarized descriptively as (1) number of applications made and (2) total amount of gel used.

For subjects applying active gel only twice per day (DDEA 2.32%), and additional compliance and exposure computation will be performed relative to the tubes and applications of active gel.

12.2.4.2 Prior and Concomitant Medications

Prior and concomitant medications will be listed in the safety population. Concomitant medications will be summarized by preferred term, and the number and percentage of subjects who took any concomitant medication, will be presented.

12.2.5 Primary Analysis(es)

The primary efficacy endpoint will be change from baseline in POM on Day 5 of treatment as assessed by a 100 mm VAS scale.

The following primary non-inferiority hypothesis will be tested for DDEA 2.32% vs DDEA 1.16%:

The null hypothesis is Diclofenac 2.32% DDEA Gel administered BID is inferior to Diclofenac 1.16% DDEA gel administered QID with the alternative hypothesis being Diclofenac 2.32% DDEA Gel administered BID is non-inferior to Diclofenac 1.16% DDEA gel administered QID.

Diclofenac 2.32% DDEA Gel administered BID will be declared non-inferior to Diclofenac 1.16% DDEA gel administered QID if the upper limit of the two-sided 95% confidence interval of the difference between their mean changes from baseline VAS POM responses is less than the established margin of 13 mm.

The primary analysis will be based on an analysis of covariance (ANCOVA) with treatment and center as factors and baseline value as a covariate to estimate the treatment difference twosided 95% confidence interval for the primary endpoint to assess non-inferiority, using the per protocol and mITT analysis populations.

Evidence of a treatment-by-center interaction will be assessed by adding a factor for this interaction in a separate additional analysis model of the primary endpoint. If there is evidence of an interaction (p<0.05), then the primary endpoint outcome will also be summarized by center for further investigation and assessment

12.2.6 Secondary Analysis(es)

Secondary outcome measures (endpoints) include:

- Change from baseline of POM on VAS on Days 3 and 8 respectively
- Tenderness measured by pressure algometry on Days 3, 5 and 8 (change from baseline and difference between the measurement in injured area and contralateral area)
- Change from baseline Ankle Joint Function (Karlsson Scoring Scale) on Days 3, 5 and 8
- Circumference measurement of swelling (change from baseline in circumference of affected ankle and comparison to non- affected ankle by Figure of Eight method on Days 3, 5 and 8)
- Pain Intensity and Pain Relief
 - Sum of Pain Intensity Difference (SPID) From hours 0 24 post first dose (corresponding to Day 1) and from hours 96 120 post first dose (corresponding to Day 5)
 - Total Pain Relief (TOTPAR) From hours 0 24 post first dose (corresponding to Day 1) and from hours 96 120 post first dose (corresponding to Day 5)

TOTPAR and SPID will be calculated as weighted sums of the Pain Relief Score and Pain Intensity Difference at each timepoint respectively:

 $TOTPAR = \Sigma R_t^x (time_t - time_{t-1})$

Where R_t = the pain relief score at time t and time t = time in hours post first dose

 $SPID_t = \Sigma PID_t (time_t - time_{t-1})(h)$

Where PI is pain intensity

- Use of rescue medication, for ankle sprain and overall
 - Total number of tablets used
 - Total number of days on which rescue medication was used

Figures will show the time course of outcomes by treatment group for key quantitative outcomes.

For POM, Karlsson score, tenderness, swelling and diary assessments (SPID and TOTPAR), an ANCOVA model including treatment group and center as main effects, and the baseline value as covariate (those outcomes for which there is a baseline) will be used for analysis, with the treatment difference and 95% confidence interval (two-sided) presented for each assessment.

Use of rescue medication (number of tablets and days used) will be compared between treatments using the CHM method (modridit scores) stratified by center, with the median treatment differences and 95% confidence intervals (2-sided) presented using Hodges-Lehmann estimation.

These secondary endpoints will be analyzed using the per protocol and mITT populations.

GlaxoSmithKline Consumer Healthcare Confidential Template Version Effective: 18-May-18 (CCR #11475) Page **54** of **64**

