1.1 Schedule of Activities

The schedule of activities table provides an overview of the subject visits and study procedures.

The investigator may schedule visits (unplanned visits) in addition to those listed on the schedule of activities, in order to conduct evaluations or assessments required to protect the well-being of the subject.

	Screening/Randomization (Baseline)	zation Study Period		
Procedure/Assessment	Visit 1 Day 1	Visit 2 Day 3	Visit 3 Day 5	Visit 4 / Early D/C Day 8 ± 1
Written Informed Consent	X			
Inclusion/Exclusion Criteria	X			
Medical History	X			
Demographics	X			
Current/Prior/Concomitant Medication Review	X	Х	Х	X
Subject Eligibility	X			
Physical Exam / Vital Signs (including height and weight)	x			Xh
Urine Pregnancy Test ^a	X			X
Laboratory Safety Tests	X ^{b,c}			X ^{b,c}
Subject Continued Eligibility		Х	Х	X
Examination of Ankle Sprain	X			
Diagnostic Testing for Ankle	Xd			
Ankle Swelling, Pain on Movement, Tenderness, Ankle Joint Function	x	Х	x	х
Randomization	Х			

GlaxoSmithKline Consumer Healthcare Confidential Template Version Effective: 18-May-18 (CCR #11475)

Page 13 of 64

	Screening/Randomization (Baseline)	Study Period		
Procedure/Assessment	Visit 1 Day 1	Visit 2 Day 3	Visit 3 Day 5	Visit 4 / Early D/C Day 8 ± 1
Adverse Events (AEs) Review	Xg	Х	X	X
Dispense Subject Diary	X	Х	X	
Weigh Study Medication	X	Х	X	X
Dispense Study Medication and Dosing Card	X			
Pain Intensity and Pain Relief (Diary) ^e	X	Х	X	Х
Apply Study Medication at Clinic by trained professional or nurse	x			
Dispense Rescue Medication	X		Xf	
Review Diary		Х	X	X
Count Rescue Medication		Х	X	X
Collect Rescue Medication, Study Medication				X
Collect Diary		Х	X	X
Study Conclusion/Subject Exit from Study				X

Footnotes:

^a Women of child bearing potential

^b Blood samples for chemistry and hematology

^c Review results to ensure that there are no clinically significant abnormalities. Local laboratory will report results to center in order to allow the Investigator to review results no later than 24 hours after blood samples being taken

^d As judged necessary by the investigator to exclude fracture of the ankle

^e Denotes subject completion of diary components

f If necessary

^g Adverse event collection commences from time of signed informed consent

h Height at Visit 1 only

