6.8 Subject Diary

A diary will be handed out to the subject at Visit 1, Visit 2, and Visit 3.

- Every time gel is applied, the subject must document the time and date of application. This includes gel applied at the clinic site
- Pain intensity and pain relief will both be assessed by the subjects every 2 hours ± 30 minutes (after starting study drug) until the subject goes to bed on the evening of Day 1. The same assessment and recording frequency will also be followed starting with the first dose on Day 5. On Day 1 and Day 5 where an assessment time point coincides with a dosing time point, the assessment of pain intensity and pain relief should be made prior to the dose. For all other time periods, pain intensity and pain relief will be assessed and recorded immediately prior to each study drug application.
- Every time rescue medication is taken (not allowed within 6 hours of Study Visits and within 12 hours of Study Visit 3), the subject must document:
 - Time and date of rescue medication
 - Number of tablets taken
 - Reason for use of rescue medication
 - $\circ\,$ Pain intensity and pain relief immediately prior to each dose of rescue medication

The Investigator or designee will ensure that all diary entries completed by the subject are legible. The Investigator will review the diary at each clinic visit. The diary handed out to subjects on Visit 1, Visit 2, and Visit 3 will be collected by the Investigator or designee at Visit 2, Visit 3, and Visit 4 (Day 8±1) respectively.

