#### 211206

Statistical Reporting and Analysis plan Draft V2.0 20JAN2021

| Object | ives   | Endpoints   |  |  |
|--------|--|---|--|--|
| •      | To assess efficacy of treatments for
swelling of affected ankle as measured
by Figure of Eight method                | Difference between circumference of affected
ankle to unaffected ankle by Figure of Eight
method on Days 3, 5 and 8 |  |  |
| •      | To assess efficacy of treatments for
effect on pain intensity as measured by
Sum of Pain Intensity Difference (SPID) | SPID from $0 - 24$ hours post first dose (Day 1) and from $0 - 24$ hours post first dose (Day 5)                          |  |  |
| •      | To assess effect of treatments for effect
on pain relief as measured by Total Pain
Relief (TOTPAR)                   | TOTPAR from 0 – 24 hours post first dose (Day 1) and from 0 – 24 hours post first dose (Day 5)                            |  |  |
| ٠      | To assess the use of rescue medication among subjects  | Number of tablets usedto treat ankle pain and overall   |  |  |
| •      | To assess the use of rescue medication among subjects  | Number of days on which rescue medication was used to treat ankle pain and overall  |  |  |
| Safety |  | · · · ·   |  |  |
| •      | To assess safety of DDEA 1.16% and DDEA 2.32% gels after 1 week of use   | Number, incidence, and severity of adverse events following dosing with study medication                                  |  |  |

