#### 4.5.3 Handling of Missing Values/Censoring/Discontinuations

As a part of missing data analysis a Multiple Imputation (MI) simulation method for imputing missing data will be conducted on ANCOVA analysis for the primary efficacy endpoints on the ITT population. This will help to assess the impact of missing data on the primary analysis.

Subjects who withdraw from the study prematurely will also be included in the statistical analyses up to the point of discontinuation.

The SAS procedure MI will be used and the details of MI procedure will be stated in the dataset specification document. If the data is monotone missing, an imputation model with regression baseline parameters will be applied, otherwise Markov Chain Monte Carlo(MCMC) will be applied. All variables included in the analysis model which are used in the primary model will be used for imputation andvalues at day 3 for the primary endpoint (For Day 5) will be included in the imputation model. To reduce the sampling variability from the imputation process, 50 datasets will be generated.

In the estimation step, separate analysis will be performed using the model mentioned for the primary endpoint statistical analysis Section 4.5.1.2.

After the completion of the estimation step SAS procedure MIANALYZE will be used to pool the estimates.

Refer APPENDIX 4 for sample SAS codes.

GlaxoSmithKline Consumer Healthcare Confidential

Page 22 of 36

No imputation is planned for missing diary card pain intensity and relief assessments.

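### Rescue totals (tablets and days) have no common window or denominator, so the amount summaries can understate use in an arm that loses heavy users early; the SAP's time-to-first-use comparison is not distorted in this way

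*Protocol*

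**What the plan says.** Protocol 12.2.6 lists two rescue endpoints, each for ankle sprain and overall: "Total number of tablets used" and "Total number of days on which rescue medication was used". It says these "will be compared between treatments using the CHM method (modridit scores) stratified by center", with Hodges-Lehmann median differences and confidence intervals. On analysis sets it says: "These secondary endpoints will be analyzed using the per protocol and mITT populations". No rate, offset or common observation window is given.

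SAP 1.2 (Table 1-2) keeps both amounts as secondary endpoints, including "Number of days on which rescue medication was used to treat ankle pain and overall". SAP 4.4.3 still summarizes the number of tablets taken. Its between-arm analysis, however, is time to first rescue use (median, log-rank, Kaplan-Meier), with non-users censored at their last available date. SAP section 5 records this change and says the Hodges-Lehmann analysis is not performed. It does not mention the stratified rank test.

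On follow-up, SAP 4.5.3 states: "Subjects who withdraw from the study prematurely will also be included in the statistical analyses up to the point of discontinuation". Protocol 6.8 says the three diaries "will be collected by the Investigator or designee at Visit 2, Visit 3, and Visit 4 (Day 8±1) respectively". The Schedule of Activities labels the last visit "Visit 4 / Early D/C Day 8 ± 1".

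**The concern.** Rescue use accumulates with time. A total compares subjects fairly only if they were watched for equally long, and here they are not. A subject who leaves at Visit 2 contributes two or three diary days. A completer contributes seven, eight or nine, and the later ones can fall after the 7-day gel course.

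If early leaving is related to heavy use, and is more common in one arm, that arm's totals fall because its heaviest users stopped being observed. Totals by arm would then look more alike than daily use really is, or could differ in the wrong direction. In a non-inferiority trial, supporting evidence pulled toward no difference flatters the test product.

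The plan already adjusts for unequal follow-up elsewhere. Compliance is a percentage of scheduled applications (protocol 12.2.4.1), and adverse events are also given per patient-week with log time at risk as an offset (SAP 4.7.1). Rescue amount has neither.

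**Working it through.** **The plan's own figures.** The documents give no figure for rescue use. The only sample-size figure is for the primary endpoint, and it reproduces: n per arm = 2 × 22² × (1.960 + 0.842)² / (13 − 5)² ≈ 119, against about 120 stated, and power at 120 is 0.804. Also 240 / 0.80 = 300. None of this is touched by the rescue point.

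**Inputs.** Daily maximum of four tablets (protocol 6.10). Visit 2 at 48 ± 4 h, so up to three calendar days. Final visit Day 8 ± 1. All usage and withdrawal rates below are assumptions, because none is stated.

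**Single subjects.**

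| Subject | Tablets | Days with rescue |
|---|---|---|
| Leaves after Day 3, 2 tablets a day | 6 | 3 |
| Leaves after Day 3, 4 a day (maximum) | 12 | 3 |
| Completer, 1 a day, ends Day 7, 8 or 9 | 7, 8 or 9 | 7, 8 or 9 |

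On tablets, the leaver at 2 a day ranks below the completer despite double the daily use. The leaver at 4 a day ranks above, but a four-fold daily rate appears as 12/8 = 1.5-fold. Misranking on tablets is possible, not automatic. On days, both leavers used rescue on every day observed, yet each scores 3 against 7 to 9.

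**Understatement of one arm's mean total.** Let w be the proportion leaving after d = 2 of 7 days.

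- Equal daily use, ratio = (1 − w) + w × d/7: 0.929, 0.893 and 0.857 for w = 0.10, 0.15 and 0.20, so 7%, 11% and 14% low.
- Leavers using three times as much per day, ratio = [7(1 − w) + 3wd] / [7(1 − w) + 21w]: 0.903, 0.821, 0.753 and 0.694 for w = 0.05, 0.10, 0.15 and 0.20, so 10%, 18%, 25% and 31% low.

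These are within-arm figures. If both arms shrank by the same factor, the ratio between arms would be unchanged and the difference would shrink by that factor. Bias in the comparison depends on how leaving differs between arms.

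**Illustration of a between-arm effect.** A simulation assumed Poisson daily tablets capped at 4, with gamma subject rates of mean 1.0 (control) and 1.5 (test). Leavers stop after Day 3, completers end on Day 7, 8 or 9 at random, and 5% of controls and 5% of light users in the test arm leave. Heavy users have 6 or more tablets by Day 3. The true 8-day difference is about 2.9-3.0 tablets and 0.8 days.

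| Heavy test users leaving | Test arm leaving overall | Raw tablet difference | Raw day difference | Tablets per observed day × 8 |
|---|---|---|---|---|
| 10% | 6.5% | 2.67 | 0.71 | 2.97 |
| 30% | 12.4% | 1.92 | 0.44 | 3.08 |
| 50% | 18.3% | 1.14 | 0.17 | 3.13 |

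With no test-arm leavers and 5% of controls leaving, the raw differences were 3.19 tablets and 0.92 days. The direction follows whichever arm loses more.

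**Final-visit spread.** At a constant rate a Day 9 total is 9/7 = 1.29 times a Day 7 total. The window is the same in both arms, so this is noise unless visit timing differs by arm.

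**Check on a per-day rate.** Suppose use falls over the week as 7, 6, 5, 4, 3, 2, 1 (relative units) and 20% leave after Day 2. The raw total is 0.8 + 0.2 × 13/28 = 0.893 of the truth (10.7% low). The per-day rate is 0.8 + 0.2 × 6.5/4 = 1.125 of the truth (12.5% high). Neither measure is safe alone.

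**The case against.** The strongest reply is that the SAP no longer rests its rescue comparison on totals. Under time to first use, an early heavy user who leaves counts as an event. SAP 4.5.2 and 4.6.1 specify no test of the totals. A reader might infer that heavy users who leave early are counted as light users in the trial's rescue comparison. The documents do not support that: the written comparison is time to first use, and on tablets the label does not hold even by example, since 12 exceeds 7 to 9. What remains is that time to first use says nothing about amount. The two amount endpoints stay in SAP 1.2, tablets are still summarized, and the status of the stratified rank test is unstated.

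Reach is also limited. Subjects without a Day 5 pain-on-movement assessment may be excluded from PP (protocol 12.2.2, SAP 4.2.2), so Visit 2 leavers matter mainly in mITT. They can enter mITT because early terminators complete the Visit 4 procedures, including that assessment (protocol 8.2.3).

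Tablets are also counted at visits and reconciled with the diary (protocol 6.10). That checks the records but adds no observation after a subject leaves.

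A reader might also infer that leaving reflects failure of the gel and so favours the worse product. That is conjecture: lack of efficacy is not a named reason in protocol 7.1 or SAP 4.2.1.

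**Conclusion.** The point holds in a limited form and is minor. The totals of tablets and days carry no common window or denominator, and leavers are cut off at discontinuation. If one arm loses more heavy users early, its amount summaries understate use, clearly for days with rescue and possibly for tablets. The same applies to any rank test of totals still run under protocol 12.2.6.

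The size of any bias in the treatment comparison cannot be derived from the documents, which give no withdrawal or rescue rates. The 7% to 31% figures should not be read as that bias: they are within-arm understatement under assumed rates. Nor does the allowance of 300 randomized for 240 evaluable supply a withdrawal rate, because non-evaluable also covers eligibility failures, poor compliance and prohibited medication. The Day 7-9 spread alone adds noise, not bias. Success depends only on Day 5 pain on movement, which is unaffected.

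**What to change.** In SAP 4.4.3:

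- Count rescue use over a fixed Days 1-7 window, with a stated rule for observed diary days (first dose to last returned diary day, capped at Day 7) and for a final visit that falls on Day 7.
- Beside the protocol-defined totals, not instead of them, report tablets per observed diary day and percentage of observed diary days with rescue, for ankle pain and overall.
- Add use by study day among subjects still observed, with the number observed each day, so that falling use over the week does not inflate leavers' rates unseen.
- If amount is compared between arms, base the comparison on the fixed-window, exposure-adjusted measure.

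Reconcile SAP 1.2 with 4.4.3 and section 5: say whether the two amount endpoints are descriptive only, whether the stratified rank test is dropped along with the Hodges-Lehmann estimate, and which analysis sets apply.

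The cost is one or two derived variables and a few tables from diary dates already collected. Rates for subjects with few diary days will be noisier.
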